**First**, as HIIT has more inherent variety, it may lead to better long-term exercise adherence with less “boredom” (one of the most common reasons cited for discontinuing exercise) and greater enjoyment than CME. Existing literature supports this hypothesis: (1) Participants randomized to HIIT reported greater enjoyment than those randomized to CME; (2) High intensity circuit training increased motivation to exercise to a greater extent than CME, despite a lower perceived exertion with CME; and (3) HIIT is associated with >20% higher adherence than CME. In a scoping review, participants preferred HIIT over CME in 5 of 6 studies, with no clear preference for HIIT or CME in the 6th . Given this evidence, we believe that PWH randomized to HIIT will have better long-term exercise adherence compared to PWH participating in CME. With the potential *substantial* benefits of long-term HIIT on physical function, fatigue, and ultimately the quality of life of older PWH, the short and long-term effects of HIIT and CME need to be examined. **Second**, coupling an exercise intervention with a theoretically-based coaching intervention is likely to enhance long-term adherence to exercise. Adherence to exercise is hard for any population, but for older PWH it may be especially challenging, and few evidence-based adherence strategies exist. Increasing self-efficacy for a healthy behavior may improve longer-term adherence. Kekäläinen et al. reported that among older (65-75 years), sedentary, community-dwelling adults who had recently completed a 9-month supervised exercise intervention, those maintaining self-directed exercise at one year had increases in self-efficacy and intrinsic motivation. Motivation has also been found to enhance medication adherence among PWH and can be modified by interventions, such as the coaching proposed in this study. By examining how supervised HIIT or CME (likely to improve exercise self-efficacy) and a tailored behavioral coaching intervention (likely to improve exercise motivation) synergize to affect long-term exercise adherence in older PWH, our study is likely to generate important novel data that will enhance the healthspan of this, and other vulnerable, populations.

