#### Exploratory Outcome Measures

1. Change in 1-RM adjusted for lean body mass from week 0-16.
2. Change in VO2 maximum from week 0-16.
3. Change in Short Performance Physical Battery (SPPB) and modified SPPB from week 0-16 and 0-28

4. Change in PROMIS-measured fatigue from week 0-16 and 0-28.
5. Change in DXA-measured total body fat and lean body mass from week 0-16.
6. Change in electron transport chain activity (skeletal muscle) from week 0-16.
7. Change in electron transport chain activity (PBMCs) from week 0-16.
8. Change in mitochondrial content (skeletal muscle) from week 0-16.
9. Change in mitochondrial content (PBMC) from week 0-16.
10. Change in physical function outcomes, patient-fatigue and physical activity adherence from week 17-28 by exercise and coaching intervention.
11. Change in mitochondrial bioenergetics, physical function and fatigue at baseline, week 16, and change from 0-16
12. Change in self-reported 3 day diet intake from week 0-16.
13. Change in stool microbiome and short-chain fatty acids from week 0-16
14. Change in muscle fat by proton density fat fraction (PDFF), intramyocellular lipid (IMCL) and extramyocellular lipid (EMCL) from week 0-16
15. Change in oxidative phosphorylation (OxPhos) from week 0-16.
16. Change in mean VO2 response *in the gastrocnemius and soleus muscles* from week 0-16.
17. Change in lean muscle quality and quantity from week 0-16 by muscle ultrasound.
18. Explore the barriers and facilitators for non-participation in an exercise-related clinical trial.
19. Change in cognitive functioning (i.e., global and domain T scores) and subjective cognitive symptoms (self-report questionnaires) from 0 to 48 weeks.
20. Change in blood markers (neurotrophins [e.g., BDNF], growth factors [e.g., VEGF], pro-inflammatory cytokines [e.g., IL-6]) from 0 to 48 weeks
21. Change in neuroimaging markers: cerebral blood flow, resting state functional connectivity, and brain volume), from 0 to 16 weeks (UAB SITE ONLY)
22. Psychological mechanisms of adherence to exercise at 48 weeks (measured with questionnaires and text message surveys)

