## COGNITIVE SUBSTUDY

Newly enrolled participants at UW/UCD sites will have the option to enroll in the cognitive substudy, which per the Timeline table above, will include cognitive assessments at current study visits (baseline, 16 weeks and 28 weeks) and a new 48 week visit which will include cognitive assessment, blood draw, and psychological mechanisms of adherence measures (which includes text messaging surveys and traditional paper pencil questionnaires). Further detail below. All enrolled UAB site participants will receive these assessments.

**Cognitive Function** will be assessed using a gold-standard battery from the National Alzheimer's Coordinating Center (NACC) Universal Data Set (UDS), which balances participant burden with acquiring a comprehensive assessment. The assessment will be conducted by staff who are blind to intervention group. Staff will be trained and certified by the study PI and will be supervised weekly via meetings and communication. 30% of batteries will undergo double scoring by another staff member and 10% of batteries will be triple scored by the study PI. The PI will also observe assessments quarterly (either in person or video).

We will examine several outcomes, including continuous composites (corrected and uncorrected for demographics) across each domain, as well as a global cognitive functioning composite. We will also examine self-reported cognitive symptoms and declines in daily function. Finally, we will use cognitive T scores and subjective symptoms and everyday functioning declines to generate cognitive diagnoses. Though there are many approaches to operationalizing cognitive impairment in HIV, and in MCI, exist, we will employ validated approaches that are consistently used in neuroAIDS. Despite subtle differences in definitions, most include mild impairment in cognitive function (e.g., ~1 SD below mean on 2 tests/domains), and evidence of either subjective cognitive deficits or declines in daily function.

| One-hour Neurocognitive Assessment Battery |  |
|--|--|
| Domain                                     | Measure  |
| Depression and Everyday Functioning        | Depression: Patient Health Questionnaire 9-item Depression; Everyday Function & Cognitive Symptoms: Functional Activities Questionnaire, Cognitive Failures Questionnaire;   |

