**Neuroimaging.** MRI data will be acquired from participants **at UAB only** (n=50) at baseline and 4 months. Participants will undergo ~1 hour of scanning at each time point, using a 3T Siemens Prisma scanner with a 64 channel coil, housed at the UAB Civitan International Neuroimaging Laboratory (CINL), where Co-I [name] is the Co-Director. Participants will be screened for any contraindications for MRI (described below in risks). We will acquire anatomical (T1 and T2 scans), arterial spin labeling (pseudo-continuous ASL), and resting state blood oxygenation level dependent (BOLD) scans. ASL, a non-invasive approach to measuring cerebral blood flow (CBF), is a MRI technique that measures tissue perfusion (blood flow), by using magnetically-labeled arterial blood water protons as an endogenous tracer. ASL has demonstrated high consistency with positron emission tomography PET measurement of CBF, and is emerging in popularity due to its advantages in terms of cost-effectiveness and safety. General quality assurance procedures will be followed as data are acquired, including quality control checks after each session. Mean global CBF, and regional blood flow to the hippocampus will be measured for each participant based on ASL scans. We will also measure changes in total gray matter volume and hippocampal volume (mm^3) using Freesurfer. Strength of connectivity within the default mode network will also be

examined based on resting state BOLD data (i.e., average correlations of BOLD-signal time series of distributed brain regions as in previous work). BOLD data will be preprocessed according to strict quality control methods, including motion scrubbing, implemented by XCP engine with fMRI prep, and regression of confounds including but not limited to motion, heartbeat and respiration.

**Psychological mechanisms of adherence (MoA)** measures will be assessed at the new 12-month visit only. The trait-level measures (i.e., paper/pencil surveys completed in person) capture aggregate perceptions about one's self, whereas text message (i.e. ecological momentary assessment [EMA]) (state-level) items reflect experiences in the moment. The measures chosen are theory-driven, align with the NIH Science of Behavior Change. As noted in the Table below, abbreviated versions of select measures used in lab visits will be used in EMA to reduce participant burden and increase compliance.

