Following the 12 month visit, the EMA will include 7-days of twice daily texts (quasi-random times at morning and evening) using their own mobile device. **Participants will already be familiar with texting procedures following the behavioral coaching intervention (part of primary study, described above and below).** The Twilio 3rd party add on feature in RedCap will be used to generate links to our RedCap survey (assessing items indicated in the Table) housed within the Denver RedCap server and text message them to participant's cell phones. No data is sent to Twilio and no PHI is collected. Twilio is HIPPA compliant and is vetted by RedCAP admin/Denver CCTSI. We piloted the survey, which takes <five minutes. If a participant does not respond to a survey, a reminder message will be sent one hour later. If a participant has not responded to any survey for 24 hours, we will contact them to troubleshoot and encourage reporting. **Actigraphy will also be worn for 7 days, using procedures described above for the Primary Study.**

We will administer individual interviews with a subset of participants (~n=25) to determine factors that drive or impede long-term PA after having been in a supervised intervention.

| Mechanisms of Adherence Measures in the New 12 month Follow Up |   |
|--|---|
| Construct  | Measure   |
| Self-Efficacy  | Lab and EMA: 9-item self-efficacy exercise (SEE) scale  assesses expectations related to ability to continue to exercise in the face of barriers (How confident are you right now that you could exercise three times per week for 20 minutes if: [e.g., "You did not enjoy it", "You were too busy", "You had to exercise alone"]?). EMA in am and pm; items use words "today" and "tomorrow".   |

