For EMA data, a linear mixed regression model including random effects for subject and day (within-subject) to account for the multilevel structure of the data will be used to examine the time-lagged effects of MoA variables occurring during a specified time interval (T-1) on PA during the subsequent (lagged) time interval (T) within each day of monitoring:  $\text{PA}(T) = \text{MoA}(T-1) + \text{Time of Day} + \text{Day} + \text{site} + \text{covariates}$ . The time interval T can be time of day or different days, for example we can use the MoA in Day 1 to predict the PA in Day 2 or use the MoA in the morning to predict the PA later in the same day. The covariates include significant distal predictors. Moderating effects will be explored by including interaction terms in above model. Concurrent effects of these MoA variables on PA (i.e., both the predictor and outcome were assessed during the same time interval) will also be examined. To explore whether the MoA variables mediate intervention (HIIT vs CME and coaching texting vs control) effects on PA, mediation analyses with focus on effect estimation rather than hypothesis testing will be conducted using path analysis with methods considering the multi-level nature of data and robust to non-normality (e.g., cluster bootstrapping), assuming a causal chain of the form: Intervention (HIIT vs CME) --> effect on MoA [as mediator] --> effect on PA. Using the estimated path coefficients, direct, indirect, and total effects will be estimated and uncertainty on these estimates be estimated computed in the form of confidence intervals. Using similar mediation approaches, we will also examine whether cognitive differences between groups at 12 months are mediated by differences in PA adherence at 12 months.

Quantitative feasibility, acceptability, and intervention fidelity outcomes will be compared across sites and exercise type using analysis of variance or chi-square tests when applicable.

Qualitative analysis will be conducted for acceptability questions at 4 months and PA barriers and facilitators at 12 months. [name] and [name] have a history of designing and analyzing data from qualitative studies. Content analysis will be used to derive themes related to barriers and facilitators to long-term PA, which will be synthesized with quantitative data to examine correlates (e.g., demographics, health).

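### With mechanism scales taken only at week 48 and 12-month activity apparently worn after the cognitive test, the cognitive substudy's exploratory mediation analyses cannot separate mediation from reverse causation

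*Combined protocol and SAP*

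**What the plan says.** Timing of the MoA scales. The Cognitive Substudy section states that these "measures will be assessed at the new 12-month visit only". Item 22 of the Exploratory Outcome Measures agrees: "Psychological mechanisms of adherence to exercise at 48 weeks (measured with questionnaires and text message surveys". No quantitative MoA scale is scheduled at baseline, week 16 or week 28.

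Timing of cognition and PA. The substudy adds "a new 48 week visit which will include cognitive assessment, blood draw, and psychological mechanisms of adherence measures". The text surveys come afterwards: "Following the 12 month visit, the EMA will include 7-days of twice daily texts". The same paragraph then says "Actigraphy will also be worn for 7 days, using procedures described above for the Primary Study". The monitor week is not dated separately, but its placement beside the post-visit surveys implies that it follows the visit.

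Analysis. The Cognitive Substudy Statistical Analysis section proposes a path analysis that assumes a chain from intervention to MoA to PA. By similar methods it will ask whether "cognitive differences between groups at 12 months are mediated by differences in PA adherence at 12 months". It also plans a lagged model in which MoA in one interval predicts PA in the next, within the survey week. The mediation work is presented as exploratory estimation, not testing.

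**The concern.** Both path models need the mediator to come before the outcome. By week 48 both interventions are over and exercise has or has not been maintained. A participant who is still exercising may report more self-efficacy and motivation because of the exercising. Some instruments build this in. The lab self-regulation scale looks back over four weeks, and its text version is skipped when no activity is reported.

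For cognition the order appears to be reversed outright: the test is at the visit and the mediator is recorded in the days after it. A participant with better cognition may find it easier to stay active.

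In both cases the wrong causal direction can produce the same path coefficients as the hypothesised one. The risk is that the substudy names a target for future interventions, such as self-efficacy, that is only a by-product of exercising, or credits PA with a cognitive effect that it did not have. No section names reverse causation, an adjustment for prior PA or prior cognition in these models, or a sensitivity analysis for the ordering.

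**Working it through.** The plan gives no effect size or power for these mediation analyses, so there is no stated figure to reproduce. The check asks how large a mediated effect appears when the true one is zero. All correlations and effect sizes below are assumptions. Variables have unit variance within arm.

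**1. MoA to PA, when MoA is only a consequence of earlier PA**

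- The intervention shifts week-28 PA by d.
- PA48 = r × PA28 + error. MoA48 = g × PA28 + error. MoA has no effect on PA.
- Path a (intervention to MoA) = g × d.
- Path b (PA48 on MoA48 within arm) = r × g.
- Total effect on PA48 = r × d.
- Apparent proportion mediated = (g × d)(r × g) / (r × d) = g².

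Result: 0.09 for g = 0.3, 0.25 for g = 0.5 and 0.49 for g = 0.7. Neither d nor r matters. Under this model, adjusting for PA28 sets path b to zero.

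**2. PA to cognition, when cognition drives PA**

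- The group difference in cognition is γ SD at each visit. PA = b × cognition at the same visit + error. PA has no effect on cognition.
- Path a (group to PA48) = b × γ. Path b (cognition on PA48 within arm) = b.
- Spurious indirect effect = γ × b². Total effect = γ. Apparent proportion mediated = b².

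Result: b = 0.2 gives 4%, b = 0.3 gives 9%, b = 0.5 gives 25%. For γ = 0.3 to 0.5 the spurious indirect effect runs from 0.3 × 0.04 = 0.012 SD to 0.5 × 0.25 = 0.125 SD.

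**3. Simulation of case 2**

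The substudy target is 60 + 50 = 110 (Study Timeline). The parent trial's 20% dropout, borrowed for illustration, leaves 110 × 0.8 = 88. Visit-to-visit correlation of cognition is assumed to be 0.8, with 4,000 runs per setting, γ = 0.3 or 0.5, and b = 0.2, 0.3 or 0.5.

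| Analysis, with no true PA effect | N = 110 | N = 88 |
|---|---|---|
| Planned order: PA–cognition path significant | 55% to 100% | 47% to 100% |
| Planned order: both paths significant | 4% to 26% | 3% to 21% |

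Mean simulated indirect effects matched the formula (for example 0.123 against 0.125 at N = 110, γ = b = 0.5).

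**4. Does an earlier mediator cure it?**

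Not by itself. With week-28 PA and no adjustment, path a = γ × b and path b = 0.8 × b, so the indirect effect is 0.8 × γ × b². If the group effect reaches week 48 only through week-28 cognition, the total is 0.8 × γ and the false proportion is still b². If the group effect stays at γ, it is 0.8 × b². Either way it is not zero.

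With week-28 PA as mediator and adjustment for week-28 cognition, the simulated mean indirect effect lay between −0.0005 and 0.0002. The PA path was significant in 4.5% to 5.7% of runs over both sample sizes, close to the nominal 5%.

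**The case against.** A reader might infer that the substudy's Aim 2 cannot be answered at all. The documents do not support that. The aim also covers distal predictors (randomised arm, demographics, changes in parent-trial outcomes) that precede 48-week PA. Its proximal part relies on real-time text surveys, for which the lagged model does order MoA before PA within the week. That model cannot place MoA before the preceding months of maintenance, but its within-week associations stand.

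The path analyses are labelled exploratory and the causal chain is openly assumed. This limits the severity, but an estimate biased by ordering stays biased whether or not it is tested.

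It is also tempting to state as fact that PA is recorded after the cognitive test. Only the text surveys are explicitly dated after the visit; for the monitor this is a strong inference. A week of wear may also stand in for a longer-standing habit. The plan neither says nor checks this, and measurement at the same visit would not establish order either.

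A reader might cite the Background remark that "those maintaining self-directed exercise at one year had increases in self-efficacy and intrinsic motivation" as the plan's own demand for change scores. That remark summarises a cited trial in the parent study's background and is not a stated rationale for the substudy.

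Some earlier mechanism data do exist. Optional interviews at weeks 0, 16 and 28 (up to 40 participants) touch on self-efficacy and outcome expectations, and a resilience scale is scheduled at baseline, week 16 and week 48. Neither supplies an earlier score on the MoA scales that enter the path models.

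**Conclusion.** The point holds for the two exploratory path analyses and no further. With every quantitative MoA scale at week 48 only, and 12-month PA apparently recorded after cognition, they cannot distinguish mediation from reverse causation. The false proportion mediated is 9% to 49% for the MoA path (g = 0.3 to 0.7) and 4% to 25% for the cognition path (b = 0.2 to 0.5). These figures assume that the whole association runs in the reverse direction; g and b are not in the documents. The chance of both cognition paths being falsely significant is much smaller than that of the PA–cognition path alone, so the main risk is a misread estimate. The randomised comparisons, the distal predictors measured earlier and the within-week lagged associations are unaffected.

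**What to change.** 1. **Cognition mediation.** Use PA already scheduled through week 28 as the mediator of week-48 cognition, adjusted for week-28 cognition, which the substudy collects. Keep the 12-month PA analysis as a concurrent association. First reconcile the Study Measures by Site table, which leaves actigraphy blank for UAB, with the Aim 3 Participants paragraph and the Cognitive Substudy text, which imply that everyone wears the monitor. If UAB has no earlier actigraphy, limit this analysis to UW/UCD: a target of 50, or 50 × 0.8 = 40 at the borrowed dropout rate. Where the data exist, the cost is analysis-plan text. The analysis then concerns PA up to week 28, and the adjustment removes any effect that PA had already had on cognition by then.

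2. **Earlier MoA scores.** For participants not yet past week 16 or 28, add the 9-item self-efficacy scale and the 19-item behavioural regulation questionnaire to the existing questionnaire sets. Use those scores, adjusted for PA at the same visit, as predictors and mediators of week-48 PA. The cost is 9 + 19 = 28 items per visit, and coverage is partial. On the targets in Table 1b, UW/UCD would have reached its 50, and UAB 30 of 60, by the end of the quarter containing the protocol's version date. Actual enrolment is not given.

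3. **Everyone else.** Adjust the week-48 MoA–PA model for week-28 PA where available, and report the result as a concurrent association, not as a mechanism or mediation. The adjustment cannot remove feedback from exercise between weeks 28 and 48, so the label is needed even with it. This changes only the analysis and its wording.

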#### D. Description, Risks and Justification of Procedures and Data Collection Tools:

**Muscle biopsy.** Participants agreeing to muscle biopsy will have a biopsy prior to and at the completion of the 16 week intervention. Participants will be advised to refrain from any physical activity for at least 48 hours following the biopsy. Non-steroidal anti-inflammatories or aspirin are held for 7 days prior to the biopsy. If participants are taking direct oral

anticoagulants, this will be held for 48 hours prior to the procedure (72 hours if creatinine clearance is 30-50 and taking dabigatran) if approved by their primary provider. Therapy can be resumed 24 hours after the procedure, or as instructed by their physician. At study completion, subjects will be asked to return within 10 days of the final exercise session for a muscle biopsy. The exercise intervention will begin >48 hours after the initial biopsy, but within 28 days. Participants will be asked to abstain from alcohol or caffeinated beverages after 1300h and to fast from any food or drink beginning at 9pm with the exception of water. The biopsy will be completed prior to 10am local time. Percutaneous samples of the vastus lateralis muscle will be obtained. After cleansing the area of the thigh with antiseptic (e.g., chlorhexidine, Betadine solution), 1% lidocaine (without epinephrine) will be injected under the skin. A 3-5 mm incision will be made in the skin and fascia over the belly of the vastus lateralis, and 100-150 mg of muscle tissue will be removed using a Bergstrom side-cutting biopsy needle with suction applied. The incision will be closed and a compression wrap and ice will be applied to the incision area for 30-45 minutes. The patient will be given instructions for wound care before discharge.

**Risks:** The risks associated with muscle biopsy include brief, mild burning pain from the local anesthetic (lidocaine), more than mild discomfort during the acquisition of tissue (about 10% of cases), and infection (less than 0.4% of cases). Allergy to the anesthetic (skin swelling or rash) occurs rarely. There may be persistent numbness in the biopsy area.

**Plan to Minimize Risk:** Risks of the muscle biopsy procedure will be minimized by having a trained clinician perform the procedure on participants who meet the biopsy-specific criteria listed above. [name] has previously performed more than 80 biopsies and [name] has completed more than 50 biopsies. Participants will be observed following the procedure for any adverse events and given strict instructions for wound care. A phone call will be made within 48-72 h of the biopsy procedure to assess wound healing with a study clinician. Additionally, the study will have a safety officer. Drs. [name] and [name] will review biopsy and exercise safety with the DSMB every 6 months.

**Justification:** Skeletal muscle mitochondria are reflective of insults that may have occurred decades earlier, whereas mitochondrial studies obtained through peripheral blood would only reflect changes over a much shorter time period. Thus the muscle specimens provide a window into mechanisms well beyond what can be collected less invasively and reflect changes in the tissue targeted with the intervention.

**Exercise testing and training:** All participants will engage in a 16-week randomized, supervised exercise intervention (high-intensity interval training [HIIT] vs continuous moderate exercise [CME], followed by a 12-week exercise maintenance intervention in which participants are also randomized to a coaching vs control intervention. The exercise prescription will be based on baseline measure of VO2 maximum (or peak) and 1-RM measurements.

**Maximal aerobic power (VO2 max).** The measurement of VO2max (or peak) will be used to formulate the prescription for CEx at the screening visit. Increases in VO2max in response to exercise training will also verify that the exercise was of sufficient intensity to induce cardiorespiratory adaptations. During an initial 5-min warm-up, walking speed will be adjusted to elicit a HR that is ~70% of maximal HR (from the screening GXT). Speed will then be held constant and the grade of the treadmill will be increased by 2% every 2 minutes until volitional exhaustion or until the test is stopped (see section 4.1.2b). The O2 and CO2 content of expired air will be measured continuously by open circuit spirometry and averaged every 30 sec using an automated online system (TrueMax 2400; ParvoMedics, Sandy, UT). Objective evidence that VO2max has been attained will include at least 2 of the following: a plateau in VO2 despite an increased energy demand, a respiratory exchange ratio in excess of 1.10, and a maximal HR within 10 beats of the age-predicted value. In the absence of these benchmarks, the maximum measured VO2 will be deemed VO2 peak.

**Muscle strength (1-RM).** Muscle strength will be evaluated as the 1-RM (the maximal weight that can be lifted only 1 time using correct lifting form through the full range of motion) for the upper and lower body REx performed during weeks 1-16. 1RMs will be measured at week 0 and every 4 weeks to week 20. The change in muscle strength from week 0 to 16 will be a secondary outcome measure.

**Exercise Intervention.** Participants will be assigned with equal probability to one of the two exercise intervention arms (high intensity interval training [HIIT] or continuous moderate intensity exercise [CME]) following completion of screening procedures. Randomization procedures will be site-specific, and use permuted blocks with stratification by sex and 10-year age categories (i.e., 50-59 years, 60-69 years, 70-80 years), to assure similar distribution in each arm. The allocation to study arm will remain blinded (masked) to the research assistant conducting the physical function assessments and to laboratory personnel.

All participants will begin with a 2-week supervised, low-intensity exercise acclimation with an experienced research assistant. The initial goal will be to walk on a treadmill for 20-30 continuous minutes at low-intensity (30-40% of maximal aerobic power [ $\text{VO}_{2\text{max}}$ ]) and complete 3 sets of 8 repetitions at low-intensity (40-50% of the one-repetition maximum; 1-RM) 3 or 4 days/week. This will facilitate comfort with study equipment and minimize injury.

At 2 weeks, all participants will complete an additional 14 weeks of moderate- intensity continuous exercise or HIIT in the University of Colorado-Denver Exercise Research Laboratory, at the Prevention Center at Fred Hutch (UW), the Center for Exercise Medicine at University of Alabama, or at a recreational center of their choosing. Weeks 1-2 will focus on familiarization with the exercises at low intensity. The intensity and duration of exercise will be progressed over the first 3-8 weeks to reach the individualized goals. The HIIT and CME interventions will be matched for exercise volume using standard equations for estimating caloric expenditure assuming 5 kcal/L  $\text{O}_2$  and 50 min/session duration for CME to meet the PA guidelines (Table 4). The total exercise time will differ by 8 minutes, but HIIT includes rest intervals and variety, which prior studies have shown is associated with greater enjoyment and physiologic benefits than CME.

**HIIT.** Following a 5-minute warm-up at 50% HRR, high and moderate-intensity exercise bouts will alternate: Five bouts of 4-minute high-intensity exercise (90% HRR) will alternate with four 3-minute bouts of moderate-intensity exercise (50% HRR). The total exercise time will be 42 minutes.

**CME.** Following a 4 minute warm-up at 50%HRR, the participant will walk for 50 continuous minutes at 60% HRR^140.

**Resistance Exercise (For Both HIIT and CME).** The initial goal will be to complete 3 sets of 8-10 repetitions of 3 exercises at low intensity (50% 1-RM) and then progress to moderate intensity (70-80% 1-RM). Exercise intensity will increase every 4 weeks or when participants can complete more than 8 repetitions with proper form at the prescribed weight. The exercises will be leg press, lateral pulldown, and a chest press, all on weight-stack equipment.

**Supervised exercise sessions.** Experienced research assistants (RA) will supervise exercise, interact frequently with participants, and encourage feedback regarding any discomfort. Participants will be instructed on maintaining a log of exercise that will be collected weekly and reviewed by Drs. [name], [name], [name], and [name]. RA observations in conjunction with the exercise session logs will be used to modify the exercise prescriptions. The individualized exercise prescriptions will be geared toward increasing the exercise stimulus while avoiding unfavorable events. Barriers to completing exercise will be discussed and solutions offered. Heart rate monitoring during each exercise session (continuously) will allow for immediate feedback on achieving target goals.

**Variety booster exercise.** Feedback during our prior intervention indicated that participants want to learn about other exercise types. Thus, in addition to the 3 sessions/week, we will provide suggestions to try a variety of other types of exercise (e.g., tai chi, yoga, elliptical, stationary bike).

**Risks:** The potential risks of exercise testing and training include development of ventricular arrhythmia, myocardial infarction, cardiac arrest, and death, as well as the less serious problems of injury to tendons, ligaments, joints, and muscles. Measures taken to minimize these risks are detailed below.

- **Endpoints for exercise tests:** In asymptomatic individuals who do not develop cardiovascular abnormalities, the endpoint for the maximal exercise tests will be achieving 85% of age-predicted maximal heart rate, fatigue that forces cessation of exercise, or increasingly unstable gait. The criteria that will be used to stop the exercise test before meeting the above criteria include the development of: (a) ST-segment depression of more than 0.2 mV that is either horizontal, downsloping, or slowly upsloping (less than 1 mV/sec) and lasts for 0.08 sec, or ST-segment elevation greater than 0.1 mV; (b) chest pain or discomfort; (c) serious arrhythmias, including multifocal PVCs, ventricular tachycardia, or sustained atrial tachyarrhythmias; (d) development of A-V block or other conduction defects; (e) a fall of systolic blood pressure of 10 mmHg or greater from the peak level with increasing exercise intensity; (f) diastolic blood pressure above 110 mmHg or systolic above 220 mmHg; (g) dizziness; (h) ataxic gait; and (i) pallor or cyanosis. If a subject is noted to have osteoporosis (T-score <-2.5, upon screening, he or she will be referred to their primary care physician to discuss the potential risks and benefits of exercise and the need for immediate or delayed treatment for osteoporosis prior to initiating the study. The risks associated with the muscular strength tests are musculoskeletal pain, fatigue, dizziness, and syncope. These risks will be minimized by providing one-on-one instruction in proper exercise

| Table 4. Example Aerobic Exercise Prescriptions                            |     |             |      |            |
|--|-----|-------------|------|------------|
| Participant weight = 78 kg and $\text{VO}_{2\text{peak}}$ = 25.2 ml/kg/min |     |             |      |            |
|  | HRR | # Intervals | kcal | Total time |
| CME   | 60  | 1 x 50 min  | 290  | 50 min     |
| HIITa (low)  | 50  | 4 x 3 min   | 288  | 42 min     |
| HIIT (high)   | 90  | 5 x 4 min   |      |            |
| a alternating low/high-intensity, starting with low-intensity   |     |             |      |            |

technique on multiple days prior to testing. Workloads will be increased gradually to elicit moderate to maximal effort, and a brief rest period will follow each attempt. Appropriate warm-up and cool-down periods will be included in the strength test procedures. Blood pressure will be monitored before and after exercise for the first 6 sessions. The potential for a serious adverse event to occur with resistance exercise testing is minimal in persons who have undergone prior medical screening. In 20,000 maximal dynamic strength tests in women and men aged 18 to 93 years, no cardiovascular events were reported .

- **Training of personnel:** All personnel assisting with the administration of screening treadmill tests and with the exercise training will have Basic Life Support certification and at least 1 member of the testing team will have Advanced Cardiac Life Support certification. In accordance with current recommendations of the American Heart Association and American College of Sports Medicine, a clinician with exercise stress testing experience in older adults or an exercise specialist technician with experience testing older adults will directly supervise screening treadmill tests; a physician will be immediately available in the facility if not directly administering these screening tests. A physician will interpret ECG and blood pressure responses for all screening treadmill tests. For subsequent exercise testing (e.g., strength testing), the physician will provide written orders, based on the results of the screening test, regarding whether a clinician must be present for, or directly supervise, the follow-up tests. For participants who decide to complete the intervention at a recreational center, all staff and employees at the location will be verified to have Basic Life Support certification, an automated external defibrillator (AED) device on hand, and an employee available at all work hours by an RA prior to the start of the intervention.
- **Screening of volunteers:** To minimize the risks of exercise testing in older subjects, testing will be conducted only after the volunteer is examined by a clinician and after a resting ECG is obtained and evaluated. During exercise testing, the ECG is monitored continuously and BP is measured frequently. Exercise tests are terminated if any of the American College of Sports Medicine absolute (and, in some cases, relative) stopping criteria are met . The American Heart Association-recommended emergency equipment and supplies will be available, including: automatic external defibrillator; portable oxygen tank, nasal cannula, ventimask, non-rebreathing mask, and appropriate tubing to connect to the oxygen tank; oral airways; bag-valve-mask hand respirator; syringes and needles; IV tubing, solutions, and stand; and adhesive tape. All exercise trainers will have current Basic Life Support certification. The Exercise Research Laboratory (ERL) at UCD-AMC, at the exercise facilities at the Prevention Center at Fred Hutchboth, and The Center of Exercise Medicine at University of Alabama operate as 911 emergency response facilities should any emergencies arise.

**Justification:** Exercise is routinely recommended in older adults for its known benefits on multiple systems. Furthermore, stress testing is a routine clinical screening test if recommending that older adults with risk of cardiovascular disease plan to begin an exercise intervention. Thus the procedures are consistent with routine clinical practice. If any injuries occur during the study, participation will be placed on hold until cleared by the participant's physician or other healthcare provider to return to full exercise. If the participant's exercise hold is longer than 2 weeks, the exercise may be gradually increased to return to the same intensity, with exercise ramp-up at the discretion of the study team and based on the reason for holding exercise.

**DXA:** Whole body densitometry (DXA) scan will be performed: Body composition comparisons will include total body fat free mass, body fat mass, trunk fat, trunk to limb fat ratio, and appendicular lean tissue mass. Determination of sarcopenic obesity will be calculated from appendicular skeletal lean tissue mass divided by squared height ( $\text{kg}/\text{m}^2$ ), with  $< 7.26 \text{ kg}/\text{m}^2$  in men or  $< 5.45 \text{ kg}/\text{m}^2$  in women suggesting presence of sarcopenic obesity based on limited prior studies.

